#### 3.2 Hypothesis

Our hypothesis is that rotavirus vaccines may increase the risk for intussusception by inducing cytokines or other inflammatory responses that affect the anatomy or functional motility of the small intestine and that there will be a relationship between the pattern of the shedding of vaccine strain rotavirus and the anatomy and or functional motility of the small intestine. We also hypothesize that potential factors such as maternal antibody, human blood group antigens and breast milk in breast-fed infants could modify rotavirus vaccine virus shedding and/or inflammation following vaccination.

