### **Potential Modifiers of Rotavirus Infection, Vaccine Response and Shedding and Intussusception Maternal Serum Antibody**

In order to examine the possible role of maternal antibody to rotavirus, we will test the initial blood sample for maternal antibody to see if maternal antibody affects shedding of vaccine virus, blood and stool cytokine responses and intestinal motility and anatomy. In addition, we will measure the infant's IgA antibody to assure that the child has not been infected with rotavirus.

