### **Secretor Status**

Thus, in an exploratory analysis, we will examine whether there is an association with secretor status and inflammatory response.

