Recruitment and enrollment will occur prior to the first study visit. There will be three scheduled study visits after recruitment/enrollment. . Infants will be randomized to either RV1, RV1 plus other immunizations, RV5 alone, or RV5 plus other immunizations. Visit 1 (day 0) will include blood, saliva, stool and breast milk collection . The MRI and ultrasound will be performed prior to vaccination. Children will receive the immunizations to which they are randomized. Imaging personnel and parents will be blinded to rotavirus vaccine type; they will be informed about other vaccines administered. A second MRI and ultrasound will be performed at Visit 2 (day 5) and blood and stool samples collected. Parents will be unblinded at the completion of Visit 3 (day 14). Arrangements will be made to get remaining doses of same rotavirus vaccine. Daily stool samples will be collected at home during the 15 day study period (on vaccination day 0 and for next 14 days). A memory aid will be completed to collect reactogenicity data on days 0 and for the next 14 days. Remaining stools and reactogenicity data from parents will be collected at Visit 3. **See Appendix 1 for detailed description of visits and timeline.**

We will assess blood and stool cytokine responses and intestinal anatomy and motility after rotavirus vaccination by comparing pre-vaccination with post-vaccination responses in the study infants. Cytokines and intestinal anatomy and motility will be assessed at baseline (Visit 1, the day of vaccine receipt) and 5 days after vaccination (Visit 2). For both blood and stool, the following cytokines will be tested: IL-2, IL-6, IL-7, IL-8, IL-15, INF- $\gamma$  and TNF- $\alpha$ . Additional biomarkers may be studied. The 5 day period post-vaccination was chosen because this time period corresponds with the peak period for intestinal replication of rotavirus vaccine virus for both vaccines.

In order to protect the health of infants, we will provide procedures to facilitate and assure that infants enrolled in the study will receive the routinely recommended vaccines for 2 month old infants which are DTaP, Hib, PCV13, HBV and IPV that will also allow them to get their 4 month vaccines on schedule.

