#### **4.4 Randomization and Study Withdrawal**

##### **Randomization Procedures**

The randomization code will be prepared by statisticians in the Epidemiology and Biostatistics Core at CCHMC. The randomization code will link to the vaccine assignment. The subject will be assigned a randomization code. Randomization will take place prior to the vaccine administration, but after the parent/legal guardian has given permission/informed consent, signed the IRB-approved consent form and met all of the inclusion and none of the exclusion criteria. Infants will be randomized 1:1:1:1 to one of four groups: 1) RV1 alone, 2) RV5 alone, 3) RV1 with routine immunizations (DTaP, Hib, PCV13, HBV and IPV or 4) RV5 with routine immunizations.

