**b) Inferential statistics**

The primary analysis for this study is the comparison of anatomical outcome as measured by MRI between (RV1, RV5 with and without other vaccines: 4 groups) and within (pre and post) study groups. The primary anatomical outcome will be the terminal ileum thickness measured in mm. The change in this outcome before and after vaccination will be compared for each study group (within group test) using a paired t-test, while the between group difference at pre, post and on the difference between pre and post (change score) will be initially analyzed using general linear model (GLM) where the ileum thickness (at pre, post and change score) is modeled as a function of group (4-groups). Depending on the result of the F-test from the GLM analysis, this will be followed by pairwise comparison between groups (6-comparisons). This will be examined using a two sample t-test. If the difference between groups with and without other vaccines for a given vaccine (RV1 or RV5) is not significant we might combine the categories and conduct a comparison test for the outcome between the two vaccine types. If the primary outcome is not normal before or after transformation we will use the non-parametric Kruskal-Wallis test to compare the groups. Although the primary between group comparisons is based on the pre-post change score, we are conducting additional analysis based on the pre and post data to get more insight about the distribution of the primary outcome variable.

We will also examine the distribution of socio-demographic and other potential covariates among the groups using a GLM analysis. If some covariates are differentially distributed among the groups, those covariates will be controlled for in the primary analysis described above. Potential modifiers such as breast milk or secretor status will be examined by modeling the primary outcome as a function of group, potential modifier and the interaction between group and modifier. In this case the parameter of interest is the coefficient of the interaction term, however it is possible that the interaction test might not be sensitive due to sample size. Regardless we will examine and report the observed change between groups for each potential modifier as a subgroup. For example we will report difference between groups in the primary outcome for secretors and non-secretors separately.

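### Section 10.3 targets whether a modifier changes the difference between vaccine arms, while the hypothesis asks whether it changes the response to vaccination; the modifier effect pooled over arms is neither designated nor reported

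*Combined protocol and SAP*

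**What the plan says.** **The question.** Section 3.2 hypothesises that maternal antibody, blood group antigens and breast milk "could modify rotavirus vaccine virus shedding and/or inflammation following vaccination". Section 3.4 repeats this by factor. Maternal antibody is measured "to see if maternal antibody affects shedding of vaccine virus, blood and stool cytokine responses and intestinal motility and anatomy"; breast-milk IgA is to be examined against shedding, cytokines, anatomy and motility; and for secretor status "we will examine whether there is an association with secretor status and inflammatory response". Exploratory objective 4 in section 3.3 asks whether these factors modify the responses.

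**The design.** Section 4.4: "Infants will be randomized 1:1:1:1 to one of four groups: 1) RV1 alone, 2) RV5 alone, 3) RV1 with routine immunizations", the fourth group being RV5 with routine immunizations. No arm goes without a rotavirus vaccine. Section 4.1 assesses cytokine, anatomical and motility responses "by comparing pre-vaccination with post-vaccination responses in the study infants".

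**The analysis.** Section 10.3 b) examines modifiers by "modeling the primary outcome as a function of group, potential modifier and the interaction between group and modifier", adding: "In this case the parameter of interest is the coefficient of the interaction term". Whatever that test shows, strata will be reported, and the example given is that "we will report difference between groups in the primary outcome for secretors and non-secretors separately". The same approach is carried to the other imaging outcomes and to cytokines, where a possible later stratified analysis is mentioned but not defined.

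**The concern.** An interaction between treatment and modifier answers an effect-modification question when one arm is untreated. Here all arms are vaccinated and the response is the change within each infant. Whether secretor status alters the response to vaccination is therefore a question about the modifier's own effect on that change. The interaction asks something else: whether RV1 versus RV5, or rotavirus vaccine with versus without routine vaccines, differs by secretor status.

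At stake is the second half of the hypothesis in section 3.2. If infants with high maternal antibody, or non-secretors, respond less whichever product they receive, the hypothesis is correct, yet the two outputs named in 10.3 would show nothing. The Power paragraph says effect sizes are to inform later studies; on modifiers, those carried forward would belong to a different question.

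**Working it through.** The documents give no power figure, alpha or SD, so there is no stated figure to reproduce.

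**1. Can the planned outputs detect a modifier that acts equally in all arms?** Take illustrative values: secretors change by +0.4 mm and non-secretors by 0 in every arm.
- Modifier effect on change: 0 − 0.4 = −0.4 mm.
- Any between-arm difference among secretors: 0.4 − 0.4 = 0. Among non-secretors: 0 − 0 = 0.
- Interaction, the difference of those differences: 0 − 0 = 0.

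Both planned outputs are zero, and no sample size alters that.

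**2. Simulation.** Four equal arms, SD 1, assumed two-sided alpha 0.05, a common modifier effect of 0.5 to 1.0 SD, modifier prevalence 23% to 50%, and 2,000 replicates per setting. The interaction was tested on 3 degrees of freedom, because four groups give three interaction coefficients rather than one.

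| N | Interaction test rejects | Modifier test (group + modifier, no interaction) rejects |
|---|---|---|
| 148 | 4.6% to 5.7% | 72% to 100% |
| 104 | 4.3% to 6.1% | 54% to 100% |

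The interaction test stays at about its null rate.

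**3. Precision, in SD units of the change score.** Inputs: N = 150 (maximum enrolment, section 4.1); N = 105 (0.70 × 150, from the both-MRIs benchmark in Appendix 2); p = 0.23 non-secretors (healthy controls in the FUT2 background section); multiplier 1.96 + 0.84 = 2.80 for assumed two-sided alpha 0.05 and 80% power. Here pq = 0.23 × 0.77 = 0.1771.
- Pooled secretor contrast: SE = √(1/(Npq)).
- Interaction for one pair of arms: SE = √(2/((N/4)pq)), variance 8 times the pooled one.
- Interaction for RV1 versus RV5 with arms combined: SE = √(2/((N/2)pq)), variance 4 times the pooled one.

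| | SE, N = 105 | Detectable, N = 105 | SE, N = 150 | Detectable, N = 150 |
|---|---|---|---|---|
| Pooled contrast | 0.232 | 0.65 | 0.194 | 0.54 |
| One pair of arms | 0.656 | 1.84 | 0.549 | 1.54 |
| RV1 versus RV5 | 0.46 | 1.30 | 0.39 | 1.09 |

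Expected non-secretors per arm: 150/4 × 0.23 = 8.6, or 105/4 × 0.23 = 6.0.

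**4. Does another part of the plan supply the missing estimate?**
- Descriptive statistics in 10.3 a) are for the whole population and by vaccine group, not by modifier level.
- Shedding is correlated with imaging in 10.3, not with modifiers, although it comes first in the modifier hypothesis.
- Maternal antibody is not named in 10.3.
- The modifier model does not say whether its outcome is the pre, post or change value. Fitted to the post value, the modifier term would mix in baseline differences.

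**The case against.** A reader might infer that the plan never estimates the modifier's effect on response. The documents do not support that. The model contains the modifier as its own term, and with the change score as outcome that term bears on the question. It describes a single arm only under reference coding, and no coding is stated; an arm-averaged estimate could be taken from the same fit. What stands is that this effect is not designated or reported.

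A reader might also infer that the trial would declare no modification. Section 10.3 does not say so. It warns that the interaction test may be insensitive and commits to subgroup results regardless. But the warning blames sample size, which is not the cause here, and the subgroup example is again a difference between groups. The stratified cytokine analysis could help, but it is optional and undefined. Maternal antibody is not excluded, since the modifiers named in 10.3 are examples.

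The interaction is a legitimate question in itself. The background leaves open whether product differences are real, and the primary objective concerns both products with and without routine vaccines. It deserves a place, though not as the sole named target.

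The eightfold variance ratio is not fixed. Section 10.3 allows arms to be combined by vaccine type, and the ratio is then four. The contrasts are also different estimands, so the ratio does not itself show an error.

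Finally, this is a pilot without a power calculation, and section 3.4 labels the breast-milk and secretor analyses exploratory. The primary anatomical comparison and the feasibility objective are untouched, which limits the severity.

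**Conclusion.** The point holds as a mismatch between question and target. The interaction and the stratum-specific arm differences address whether a modifier alters the contrast between vaccine arms; sections 3.2, 3.3 and 3.4 ask whether it alters the response after vaccination. That conclusion rests only on every arm being vaccinated, not on any power figure. The detectable effects show scale and depend on the assumed alpha, power, non-secretor share, evaluable numbers and a normal approximation.

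The matter is exploratory and should be corrected before analysis. Even when corrected, the results are associations, because the modifiers are not randomised. For anatomy and cytokines, the lack of an unvaccinated arm also means that vaccine response cannot be separated from other change between visits.

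**What to change.** In section 10.3:

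1. Make the arm-adjusted modifier effect on the change score the exploratory target, from a model with group and modifier and no interaction. Give its 95% CI, report mean change by modifier level, and state that the outcome is the change score.
2. Name maternal IgG and keep it continuous. Fit breast-milk IgA only among breastfed infants with a sample, since sections 3.4 and 6.2 collect milk only from breastfeeding mothers. Use feeding status as the modifier for all infants.
3. Add an arm-adjusted modifier analysis for shedding: ordinal for the none, low and high categories of section 3.4, or logistic for detection. A linear model does not suit these data, because section 6.4 quantifies only positive Visit 2 stools.
4. Keep the group-by-modifier interaction and the stratum-specific arm differences as secondary.
5. State that all modifier results, shedding included, are associations, and add the limit from having no unvaccinated arm for anatomy and cytokines.

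Cost: a few sentences in 10.3. No new data and no change to randomisation, visits or sampling.

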#### 3.3 Primary and Exploratory Objectives

Primary Objectives:

- 1) to examine the effects of RV1 and RV5 with or without other routine immunizations on gastrointestinal anatomy
- 2) to assess the feasibility of conducting a larger scale study

Exploratory Objectives:

- 1) to examine the effects of RV1 and RV5 with or without other routine immunizations on gastrointestinal motility
- 2) to examine the effects of RV1 and RV5 with or without other routine immunizations on blood and stool cytokines and inflammatory responses, including clinical reactogenicity events
- 3) to assess patterns and level of vaccine virus shedding after RV1 and RV5
- 4) to provide preliminary data assessing associations with the pattern of rotavirus vaccine strain (RV1 and RV5) shedding in the stool and blood, stool cytokine responses, and the anatomy and/or functional motility of the small intestine; and examine other factors such as maternal antibody, breast milk antibody, and human blood group antigens to see if these factors modify these responses
- 5) to compare MRI and ultrasound imaging

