### **Rotavirus Vaccine Virus Shedding**

We will use RT-PCR to identify rotavirus vaccine strains, to examine the duration of shedding and to quantitate rotavirus shedding 5 days post-vaccination. We will then assess the correlation of the amount of virus shedding with intestinal anatomy and motility as well as cytokine and inflammatory responses. The Ct values will be examined and categorized as none, low or high for analysis. We chose 14 days to assess the duration of shedding since studies have shown that most vaccine-associated events occur in the first 14 days and shedding becomes less frequent after 14 days. Vaccine virus shedding (qualitative) will be done on all stools collected. In addition, since we will be collecting reactogenicity data for Days 0-14, stool from other days could be evaluated for stool cytokines should the infant have an adverse event either before or beyond the Visit 2 stool evaluation.

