## **4 Research Plan**

### **4.1 Overview of Study**

This study is a prospective clinical study designed to 1) examine the effects of RV1 and RV5 alone or with other routine immunizations on gastrointestinal anatomy 2) to assess the feasibility of conducting a larger scale study. Exploratory objectives include 1) to examine the effects of RV1 and RV5 with or without other routine immunizations on gastrointestinal motility 2) to examine the effects of RV1 and RV5 with or without other routine immunizations on blood and stool cytokines and inflammatory responses, including clinical reactogenicity events 3) to assess patterns and level of vaccine virus shedding after RV1 and RV5 4) to provide preliminary data assessing associations with the pattern of rotavirus vaccine strain (RV1 and RV5) shedding in the stool and blood, stool cytokine responses, and the anatomy and/or functional motility of the small intestine; and examine other factors such as maternal antibody, breast milk antibody, and human blood group antigens to see if these factors modify these responses and 5) to compare MRI and ultrasound imaging.

Healthy infants 6-13 weeks of age will be randomized (1:1:1:1) to receive either, RV1 alone, RV5 alone, RV1 with ACIP routinely recommended immunizations (Diphtheria, Tetanus and Pertussis (DTaP), *Haemophilus influenzae* type b (Hib), pneumococcal conjugate (PCV13), Hepatitis B (HBV) and

inactivated polio (IPV)) or RV5 with routine immunizations. Imaging study personnel and parents will be blinded to the rotavirus vaccine type; parents will be informed about the rotavirus vaccine type at the completion of the study. Up to 150 infants will be enrolled (see inclusion/exclusion below). The age-group of infants 6-13 weeks of age was chosen so enrolled infants can receive their first dose of rotavirus vaccine at the AAP/ACIP recommended age of 2 months (minimum age of 6 weeks and maximum age of 14 weeks and 6 days) and, to assure that other ACIP recommended vaccines can be administered at the recommended age.

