To assess how vaccine shedding is related with the primary outcome by looking at the correlation between the imaging outcome and the fecal shedding for each group (using sample obtained close in time with the imaging). This will be examined using Pearson or Spearman correlation coefficients based on the normality of the data. The resulting correlation coefficient from each group can be compared with each other (pairwise) using Fisher's transformation and compare the resulting z-scores. If the correlation are not different we may then combine the groups and run the correlation across group to get an insight on the relationship between shedding and imaging parameter.

For all the other imaging parameters (cecum thickness, wave pattern and amplitude) similar analysis described for the primary outcome (ileum thickness) will be conducted. For Lymph node presence a logistic regression instead of GLM, and for the lymph node number, and wave frequency a Poisson regression will be used.

For the cytokines outcome (IL2, IL6, IL7, IL8, IL15, TNF) similar analysis described for the primary imaging outcome including examination of modifying variables and potential subsequent stratified analysis will be conducted.

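### Pooling the shedding and imaging data across arms without an arm term could create or mask a correlation if arms differ in mean on both variables

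*Combined protocol and SAP*

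**What the plan says.** Section 10.3, part b (Inferential statistics), sets out three steps for relating fecal shedding to the imaging outcome.

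- A correlation in each group: "This will be examined using Pearson or Spearman correlation coefficients based on the normality of the data".
- A comparison of the group coefficients, which "can be compared with each other (pairwise) using Fisher's transformation". With four groups there are six pairs.
- Then the combined analysis: "If the correlation are not different we may then combine the groups and run the correlation across group". Its stated purpose is to gain insight into the relationship.

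No partial correlation, stratification, centring within arm or group term is named for the last step. The same part of section 10.3 does provide for covariates that are unevenly distributed, but "those covariates will be controlled for in the primary analysis described above", which refers to the linear model for ileum thickness and not to this correlation.

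On the variables: "The primary anatomical outcome will be the terminal ileum thickness measured in mm". For shedding, section 3.4 says "The Ct values will be examined and categorized as none, low or high for analysis".

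**The concern.** Finding that the arm correlations are alike does not justify pooling the raw data. A correlation over the combined infants has two sources: the association among infants within an arm, and the line-up of the arm means. Only the first bears on whether an infant who sheds more shows more bowel change. The second reflects any way in which the vaccines differ.

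Equal arm means cannot be taken for granted, because the trial sets out to examine both. An exploratory objective in section 3.3 is "to assess patterns and level of vaccine virus shedding after RV1 and RV5", and a primary objective concerns the effects of the same vaccines on anatomy. The same reasoning applies to differences between arms with and without the routine vaccines.

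At stake is a wrong coefficient for a relationship that section 3.2 states as part of the hypothesis. Section 10.3 (Power) also says that effect sizes will be reported to help design later studies, so a distorted value could be carried forward.

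**Working it through.** The plan states no alpha, power or effect size for this analysis, so there is no figure of its own to reproduce.

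**Inputs from the documents**
- Sample size: "Up to 150 infants will be enrolled" (section 4.1). 150/4 = 37.5, taken as 37 per arm, N = 148.
- Lower scenario: the Appendix 2 benchmark of 70% completing both MRIs. 0.70 × 150 = 105, taken as 26 per arm, N = 104.
- Allocation 1:1:1:1 (section 4.4), so half the infants receive RV1 and half RV5.

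**Assumptions not in the documents**
- Normal data, common within-arm SD, two-sided 5% tests.
- Pooling only if all six Fisher comparisons are non-significant.
- RV1–RV5 mean differences dx (shedding) and dy (imaging), in within-arm SDs.

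**Expected pooled correlation.** With equal halves, the between-vaccine part adds 0.25·dx·dy to the covariance, and 0.25·dx² and 0.25·dy² to the variances:

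r_pooled = (r_within + 0.25·dx·dy) / √[(1 + 0.25·dx²)(1 + 0.25·dy²)]

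For r_within = 0, dx = 1, dy = 0.5: 0.125 / √(1.25 × 1.0625) = 0.125 / 1.1524 = 0.108. If dx or dy is 0, the numerator is 0 and there is no bias.

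**False-positive rate.** Approximately Φ(m − 1.96) + Φ(−m − 1.96), with m = atanh(r_pooled)·√(N − 3). For the same case:
- N = 148: m = 0.109 × √145 = 1.31, giving 26%.
- N = 104: m = 0.109 × √101 = 1.09, giving 19%.

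Simulation of the whole rule, with true within-arm correlation 0, gives:

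| dx / dy (SD) | Expected pooled r | Crude test, 37 per arm | Crude test, 26 per arm |
|---|---|---|---|
| 1 / 0 | 0 | 5% | 5% |
| 0.5 / 0.2 | 0.02 | 6% | 5–6% |
| 0.5 / 0.5 | 0.06 | 11% | 10% |
| 1 / 0.5 | 0.11 | 26% | 20% |
| 1.5 / 0.5 | 0.15 | 42% | 31% |
| 1.5 / 0.8 | 0.22 | 80% | 65% |

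The correlation adjusted for the four arms stays at about 5% in every row. Spearman gives nearly the same results as Pearson in the scenarios where both were run.

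**Three-level shedding.** With assumed none/low/high proportions of 20/30/50% for one vaccine and 60/30/10% for the other, dy = 0.5, and the Fisher step left out, the crude Spearman test is significant in 28% (N = 148) and 22% (N = 104) of trials.

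**The Fisher comparison gives no protection.** Adding a constant to every value in an arm leaves that arm's correlation unchanged, so the comparison behaves the same whatever dx and dy are. In simulation, pooling is allowed about 80% of the time in every scenario. The comparison is also weak for its own purpose: for correlations of 0 and 0.5 in two arms, z difference / SE = 0.549 / √(2/34) = 2.26, which is 62% power at 37 per arm; at 26 per arm it is 46%.

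**Masking.** With r_within = 0.20, dx = 1 and dy = −0.8, the numerator is 0.20 + 0.25 × 1 × (−0.8) = 0. The pooled correlation vanishes although every arm has a real one.

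**The case against.** Several points on the other side stand.

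- Both the Fisher comparison and the pooling are worded as options, and the pooled coefficient is offered for insight, with no test or alpha attached.
- The analysis belongs to exploratory objective 4 of a pilot. The primary analysis, ileum thickness within and between groups, is untouched.
- The bias needs mean differences on both variables. For modest differences it is negligible: a pooled r of 0.02 and a rate of about 6%.
- 37 per arm is the ceiling. Quantitative PCR is planned only for a positive Visit 2 stool (section 6.4), so fewer infants may have quantitative values.
- The four arm correlations are computed first, and imaging and fecal variables are summarised by group (section 10.3, part a), so an attentive reader could notice that the vaccines differ on both.

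It might also be argued that a vaccine difference on both variables is itself a mechanistic signal. But RV1 and RV5 differ in more than shedding, so a contrast of their means cannot attribute bowel change to shedding. That contrast should be shown as such, not folded into a correlation among infants.

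These points limit the size and certainty of the problem. None of them corrects the pooled coefficient. Leaving the step optional also means that the choice is made after the data are seen.

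**Conclusion.** The concern holds as a conditional one. The rule permits a crude correlation over all arms, and the condition placed on it cannot detect the circumstance that makes it misleading. If arms differ in mean on both shedding and the imaging outcome, the pooled value could create an association or hide one. With zero within-arm correlation, normal data and two-sided 5% tests, the false-positive rate ranges from near nominal to 80% at 37 per arm and to 65% at 26 per arm. Where the trial would fall in that range is unknown, because the documents give neither mean difference.

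A reader might infer more: that the plan will pool, that pooling will turn a brand difference into a finding of more shedding with more bowel change, and that the trial's central claim is therefore unsound. The documents do not support this. Pooling is optional, the direction depends on the signs of two unknown differences, and the analysis is exploratory. It still merits correction, because the shedding–anatomy relationship is part of the hypothesis and the change costs almost nothing.

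**What to change.** Replace the pooling sentence in section 10.3, part b, with wording to this effect: the four arm-specific correlations will always be reported with confidence intervals, together with one overall within-arm estimate, namely the correlation adjusted for arm. This would be a partial Pearson correlation, or a partial or stratified Spearman correlation on ranks, which suits the heavily tied none/low/high shedding categories.

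An inverse-variance average of the four Fisher z values is an alternative. It agrees only approximately with the arm-adjusted correlation, and its usual variance is doubtful with so many ties.

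Remove both the condition that pooling follows a non-significant comparison and the crude pooled correlation. The pairwise Fisher comparisons may stay as description.

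The cost is one sentence in the plan. No added data, visits or infants are needed, and the team keeps the single overall summary it wants.
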